APPENDIX C: ECOG PERFORMANCE STATUS

ECOG Performance Status Scale	
Grade	Descriptions
0	Normal activity. Fully active, able to carry on all pre-disease performance without restriction.
1	Symptoms, but ambulatory. Restricted in physically strenuous activity, but ambulatory and able to carry out work of a light or sedentary nature (e.g. , light housework, office work).
2	In bed <50% of the time. Ambulatory and capable of all self-care, but unable to carry out any work activities. Up and about more than 50% of waking hours.
3	In bed >50% of the time. Capable of only limited self-care, confined to bed or chair more than 50% of waking hours.
4	100% bedridden. Completely disabled. Cannot carry on any self-care. Totally confined to bed or chair.
5	Dead.

Source: Oken MM, Creech RH, Tormey DC, Horton J, Davis TE, McFadden ET, Carbone PP. 1982. Toxicity and response criteria of the Eastern Cooperative Oncology Group. *Am J Clin Oncol* 5:649-655.

APPENDIX D: SICT QUESTIONNAIRE

The combination of scores for each domain, as well as disease (Thalassemia having the worst adherence), age, missed doses have a high correlation with Non-Compliance.

SICT item Satisfaction domain

All SICT Item responses are averaged along the response scale from 1 to 5 such that a higher satisfaction domain score indicates a high level of satisfaction.

Perceived Effectiveness of ICT (6 items) (lower scores in this domain indicative of non-compliance)

Acceptance of ICT (5 items) (higher scores in this domain indicative of non-compliance)

Burden of ICT (5 items) (higher scores in this domain indicative of non-compliance)

Side Effects of ICT (3 items) (higher scores in this domain indicative of non-compliance)

The SICT used here is modified to exclude questions where there was no significant association, above.

Scoring:

1. A total score for each domain would be calculated using an adjusted mean % score, compared to the total possible score of 100%.
2. Consideration for age is judgmental – adolescents suggested with lower compliance.
3. Higher number of missed doses is suggestive of non-compliance.

DisperSol Technologies, LLC
Protocol Number: DST-0509-201 Subject Initials: _____ Subject #: _____ Date: _____

Eligibility Visit SICT Questionnaire

Instruction:

This questionnaire is intended to assess your Satisfaction with Iron Chelation Therapy (SICT) Quality of Life (QoL). Please rate the following questions on a scale of 1 – 5 as best as you can. Additional details regarding the scale are included within each section. Please only answer each question once.

Group 1: Perception of Health

< Strongly Disagree.....Neutral.....Strongly agree> 1 2 3 4 5		Patient Rating
1.	In the past three months, did you feel your current chelation therapy would help with a longer life?	
2.	In the past three months, did you feel your current chelation therapy would reduce your excess iron?	
3.	In the past three months did you feel your chelation therapy would stop your condition from getting worse?	
4.	In the past three months, did you think your chelation therapy was actually working?	
5.	In the past three months, did you feel that chelation therapy was worthwhile?	

Group 2: Acceptance of Therapy

		Patient Rating
1.	In the past three months, how would you rate the ease for you to take your chelation therapy? <Easy.....Difficult> 1 2 3 4 5	
2.	In the past three months, did you think chelation therapy was as difficult as you expected? < Easy.....Difficult> 1 2 3 4 5	
3.	How would you rate how convenient it was to take chelation therapy? < Convenient.....Inconvenient> 1 2 3 4 5	
4.	In the past three months, did chelation therapy meet your expectations? < Fully Met.....Not Met> 1 2 3 4 5	

DisperSol Technologies, LLC
Protocol Number: DST-0509-201 Subject Initials: _____ Subject #: _____ Date: _____

5.	Were you satisfied or dissatisfied with the form of your chelation therapy (oral pill/capsules or pump)? <Satisfied.....Dissatisfied>	
	1 2 3 4 5	

**Group 3:
Burden of Therapy**

	< Never.....Always>	
	1 2 3 4 5	Patient Rating
1.	In the past three months, how frequently did your chelation therapy limit your after-hours or night-time activities?	
2.	In the past three months, did you feel that your chelation therapy limited your daytime activities or routine?	
3.	How often did you feel your that your chelation therapy prevented you from getting a good night sleep?	
4.	How often do you feel that chelation therapy made you depend on others?	
5.	How disturbed were you with how much time it took to take your chelation therapy?	

**Group 4:
Side Effects of ICT**

	< Never.....Always>	
	1 2 3 4 5	Patient Rating
1.	In the past three months, how frequently were you concerned about the side effects of your chelation therapy (e.g., pain, nausea)?	
2.	How often did you feel that chelation therapy had a bad effect on your personal appearance?	
3.	Did you feel pain because of your chelation therapy?	

To be Completed by the Site Staff:

Patient Disease: (Thalassemia, SCD, MDS)	
Number of doses missed in last 7 days	

The Following references were used in the development of the SICT questionnaire:

1. Development and Scoring of the Satisfaction with Iron Chelation Therapy Instrument for Patients with Iron Overload
Rofail D¹,Viala M²,Abetz L³, Gait C⁴
¹Mapi Values Limited, Macclesfield, UK, ²Mapi Values France, Lyon, France, ³Mapi Values Limited, Bollington, UK, ⁴Mapi Values Ltd, Macclesfield, UK
2. Satisfaction with iron chelation therapy and its impact on adherence in patients with Beta Thalassemia Major: Results From the Ithaca Study
Rofail D¹, Ravera S², Scalone L³, Cappellini M⁴, Mantovani LG⁵

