4.1 Inclusion Criteria

1. Written informed consent obtained prior to any study-related procedure being performed;
2. Patients at least 18 years of age or older at the time of consent;
3. Patient with TDT or NTDT syndromes and iron overload currently receiving iron chelation therapy with Jadenu or Exjade and demonstrating inadequate response assessed with serum ferritin and LIC;
4. Stable dosing with Jadenu or Exjade for >3 months prior to screening and receiving the maximal dose (Jadenu: 28 mg/kg or Exjade: 40 mg/kg);
5. Serum ferritin levels that are persistently >800 mcg/L determined by 2 separate assessments during screening over the previous 2-4 weeks prior to study treatment and not showing a decreasing trend over these weeks;
6. An LIC of >5 mg Fe/g dw measured by MRI in the 52 weeks prior to study entry;
7. Compliant with chelation therapy in the 3 months prior to enrollment as assessed by the Investigator:
 - a. Satisfaction with Iron Chelation Therapy (SICT) Quality of Life (QoL) composite score $\geq 60\%$, or determined by investigator that at least 75% of medication prescribed on a regular basis was taken (Investigator enquiry into patient prescription refill records, preferably 3 months if available); and
 - b. Willing to comply with chelation therapy for the duration of the study;
8. Agree not to use other anti-chelating agents concurrently;
9. Eastern Cooperative Oncology Group Performance Status (ECOG PS) of 0-1;
10. Women of childbearing potential (WOCBP) must use an adequate method of birth control (double barrier, e.g. hormonal control and barrier contraception) at least 28

days prior to the first administration of the study drug, during the study and for at least 30 days after the last dose of the study drug. (Section 7.5 for details);

11. Male patients whose partners are WOCBP must use an adequate method of birth control (double barrier control) at least 28 days prior to the first administration of the study drug, during the study and for at least 30 days after the last dose of the study drug; and
12. Patient is willing and able to comply with all protocol required visits and assessments.

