4.2 Exclusion Criteria

1. Patients with life expectancy less than 6 months;
2. Females of childbearing potential not on an adequate method of birth control, or who are pregnant or lactating;
3. History of non-compliance with chelation therapy (determined by the investigator, persistently taking less than 75% of prescribed dose in the 3 months prior to enrollment, or as determined by the Investigator based on medical history, SICT QoL overall score <60% or score in any SICT domain <50%);
4. Screening blood counts of the following:
 - a. Absolute neutrophil count < 1500/ μ L
 - b. Platelets < 100,000/ μ L
 - c. Hemoglobin < 8 g/dL; transfusion support is permitted;
5. Screening chemistry values of the following:
 - a. Alanine aminotransferase (ALT) and aspartate transaminase (AST) > 2.5 \times upper limit of the normal reference range (ULN)
 - b. Total bilirubin > 2 \times ULN
 - c. Creatinine > 1.5 \times ULN
 - d. Urine protein/creatinine ratio (UPCR) >0.5 mg/mg
 - e. Albumin < 2.8 g/dL;
6. History of congestive heart failure New York Heart Association (NYHA) class III or IV or uncontrolled hypertension at screening;

7. History of other malignancy within the previous 3 years, except basal cell or squamous cell carcinoma, or non-muscle invasive bladder cancer;
8. In the opinion of the Investigator, evidence of major inflammatory disease that would affect ferritin levels within 14 days prior to the start of study medication;
9. Major surgery within 30 days prior to the start of study medication;
10. Serious persistent infection within 14 days prior to the start of study medication;
11. Serious concurrent medical condition including central nervous system (CNS) disorders;
12. Requires concomitant treatment with systemic corticosteroids, or any other immunosuppressive agents, or has used such treatment in the past 10 days before study entry (use of prednisone or equivalent <10 mg/day orally or use of inhaled corticosteroids or topical steroids is permitted).
13. Previous history of difficulty swallowing oral medications;
14. Any condition that, in the opinion of the Investigator, would impair the patient's ability to comply with study procedures or study medication; or
15. Concomitant treatment with medications described in [Section 7.4](#) "Prohibited Medications".

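### Appendix D contradicts itself and the eligibility criteria on the direction of the SICT score, and a literal reading inverts the SICT screen in three of four domains

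*Protocol*

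**What the plan says.** Protocol Section 4.1, no. 7a, accepts a patient as compliant on either of two routes: a SICT composite of at least 60%, or "determined by investigator that at least 75% of medication prescribed on a regular basis was taken". Section 4.2, no. 3, lists as history of non-compliance a persistent intake below 75% of the prescribed dose or, as the investigator determines from medical history, "SICT QoL overall score <60% or score in any SICT domain <50"%. The synopsis repeats both criteria. In both, a high score is good and a low score is bad.

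Appendix D gives the scoring. It says item responses are averaged "such that a higher satisfaction domain score indicates a high level of satisfaction". It then annotates each domain. One note runs the same way as the cut-offs: "Perceived Effectiveness of ICT (6 items) (lower scores in this domain indicative of non-compliance"). The other three do not: "Acceptance of ICT (5 items) (higher scores in this domain indicative of non-compliance"), with the same remark for Burden and for Side Effects. The domain score is called an adjusted mean percentage of the possible total; the adjustment is not explained.

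On the form, Group 1 runs from strongly disagree (1) to strongly agree (5) on favourable statements. Group 2 runs from favourable to unfavourable, for example "< Easy.....Difficult> 1 2 3 4 5". Groups 3 and 4 run from never (1) to always (5) on unfavourable statements. No item is marked for reversal.

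**The concern.** A percentage cut-off needs a defined direction. Here the criteria and one sentence of Appendix D say that high is good, while the notes and anchors for three of the four domains say that high is bad. Two sites could score the same form in opposite ways, and each could cite the appendix.

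The trial studies inadequate response despite compliance, and its pharmacokinetic hypothesis attributes that response to low exposure on current therapy. Prior non-adherence is the obvious rival explanation. The SICT is one of the tools meant to rule it out, and it is given once, at the eligibility visit (Section 6.2). Because it acts before randomisation in a study of at most 36 patients, a scoring error cannot be repaired at the analysis stage.

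**Working it through.** The plan gives no worked SICT score to reproduce, so the check is to score hypothetical patients on the printed form and apply the printed cut-offs.

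**Inputs.** Cut-offs from Sections 4.1 and 4.2: composite 60%, any domain 50%. Ratings 1 to 5 and anchors from the Appendix D form. Printed items per group: 5, 5, 5, 3.

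**Assumption.** The protocol does not define the adjusted mean %. I take domain % = 100 × mean rating / 5 and composite = mean of the four domain percentages. The profiles are illustrations, written as the rating in Groups 1, 2, 3, 4.

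**Literal reading, no reversal:**

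| Profile | Domain % | Composite % | Against the SICT thresholds |
|---|---|---|---|
| Most satisfied (5,1,1,1) | 100/20/20/20 | (100+20+20+20)/4 = 40 | Fails overall and three domains |
| Mildly satisfied (4,2,2,2) | 80/40/40/40 | (80+40+40+40)/4 = 50 | Fails overall and three domains |
| Neutral on effect, worst elsewhere (3,5,5,5) | 60/100/100/100 | (60+100+100+100)/4 = 90 | Clears all |
| No perceived effect, worst elsewhere (1,5,5,5) | 20/100/100/100 | (20+100+100+100)/4 = 80 | Fails on Group 1 only |

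The last row limits the claim: a heavily burdened patient clears the thresholds only if Perceived Effectiveness is at least 50%.

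**Sensitivity to the assumption.** Weighting by item, (5,1,1,1) gives (25+5+5+3)/90 = 42% and (3,5,5,5) gives (15+25+25+15)/90 = 89%. With domain % = 100 × (mean − 1)/4, (5,1,1,1) gives 100/0/0/0, composite 25%, and (3,5,5,5) gives 50/100/100/100, composite 87.5%. Using 6 Group 1 items instead of 5 changes no decision. Across these variants the most satisfied patient scores 25 to 45% overall and fails, and (3,5,5,5) scores 84 to 90% and passes.

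**With Groups 2 to 4 reversed (6 minus rating), mean/5.** (5,1,1,1) becomes (5,5,5,5): 100% throughout, passes. (3,5,5,5) becomes (3,1,1,1): 60/20/20/20, composite (60+20+20+20)/4 = 30%, fails. The thresholds then run as the criteria intend.

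**The scaling matters too.** An all-neutral patient (3,3,3,3) scores 60% on mean/5 and meets the composite threshold, but scores 50% on (mean − 1)/4 and falls below it. That is a second reason to define the adjusted percentage.

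**Consistency of the text.** If the domain notes refer to final domain scores, they contradict the sentence that higher means more satisfied, and the cut-offs are inverted. If they refer to raw ratings, a reversal is needed and none is written. On either reading the appendix is deficient.

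**The case against.** The best defence is that reversal was intended. The sentence equating a higher domain score with satisfaction, the word *adjusted* and the direction of the cut-offs all fit a score with Groups 2 to 4 reversed, and the notes could describe raw ratings. This stands as a plausible account of intent. It does not supply the missing step, and the notes speak of scores in the domain.

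A reader might infer that the thresholds definitely run the wrong way, so that satisfied, adherent patients are turned away and non-compliant ones enrolled. The documents do not support that:

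- The inversion depends on the unreversed reading.
- The SICT measures satisfaction, not doses taken, so a satisfied patient is not thereby an adherent one.
- Exclusion 3 has its own limb for intake below 75%, whatever the SICT score, and its SICT limb is worded as an investigator determination. Appendix D also looks at missed doses.

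These are real but partial safeguards: judgement that rests on a score of undefined direction is only as good as the score.

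A reader might also infer bias in the treatment comparison. None is shown. The comparison is within patient, dosing is observed at clinic visits and pills are counted in both periods, and any improvement in adherence would be expected on either product. The sample size rests on safety, with chelation activity described as preliminary.

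On the two routes, an inclusion criterion met alongside an exclusion criterion met is not in itself a contradiction. Read mechanically, though, exclusion 3 empties the medication route in 7a. The heading gives Perceived Effectiveness six items and the form prints five. This is minor, and the stated removal of some questions may explain it.

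**Conclusion.** The point holds as an unresolved contradiction in an eligibility instrument. The criteria treat low SICT scores as non-compliance, Appendix D says both that high is good and, for three of four domains, that high is bad, and no reversal is specified. A site that applied the form, notes and cut-offs literally would place the most satisfied patient at 40% (25 to 45% across the scalings and weightings tried) and within the exclusion thresholds. It would pass a patient with the worst answers in Groups 2 to 4 at 90% (84 to 90%), provided Perceived Effectiveness reached 50%.

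Confidence in the contradiction is high. The percentages are illustrations on an assumed scaling, although the direction did not change under any variant. How many patients would be misclassified is not known, and the effect on the treatment comparison is a plausible but unquantified risk. The defect should be corrected before the score is used to admit or exclude anyone.

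**What to change.** In Appendix D:

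- State that every rating in Groups 2, 3 and 4 is replaced by 6 minus the rating before domain and composite percentages are computed.
- Define the adjusted mean %: the scaling, and whether the composite is weighted by item or by domain.
- Tie the three notes on higher scores to raw ratings, or delete them.
- Correct the Group 1 item count.

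In Sections 4.1 and 4.2 and the synopsis, reconcile inclusion 7a with exclusion 3, so that a patient who qualifies on the medication route is not removed on SICT alone unless the sponsor intends that and says so.

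The cost is a scoring line and aligned criteria in an amendment, plus re-scoring of any forms already collected. No new assessment is needed.
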